### **Protection Against Risk**

**Confidentiality.** To minimize the possibility that a breach in confidentiality will occur, data for this study will be kept separate from any subject identifiers and will be kept in a locked file cabinet and on a secure, encrypted data management server. Digital audio and video recordings of child/parent participation in study sessions will also be uploaded on a secure, password protected computer server that is backed up by the university's main computer system. Only the PI, Co-I, PM, and designated research assistants will have access to the data. Computers where data will be entered will be accessed through passwords and kept in locked offices. Data monitoring will occur in three stages: 1) field editing for missing data by evaluators; 2) office editing by a designated research assistant after instruments are returned to the office; and 3) listening to random samples of 25% of the audio-taped evaluation sessions and video-taped intervention sessions by the PI or Co-I.

**Fatigue.** Intervenors and evaluators will be trained to observe for increasing fatigue and ask parents' to indicate if the child's or their own fatigue is at a level where the activity should be stopped. Also, intervention sessions or control condition sessions, and evaluations will be stopped if the intervenor or evaluator assesses a level of fatigue in the child or parent that precludes their ability to participate. Children and parents will be informed they can stop the session at any time and/or stop their involvement in the study at any time.

**Psychological Discomfort.** Intervenors and evaluators will receive specific training in identifying and responding to psychological discomfort related to group assignment and to evaluation. Parents and children will be informed they can stop the session at any time and/or stop their involvement in the study if they become uncomfortable. Should psychological discomfort be identified, a protocol will be in place to notify the PI. The attending oncologist and nurse on the unit will also be notified of the concern in order to make a decision regarding referral. The PI or Project Manager will follow up within 24 hours on decisions made. Should any child give any indication the level of psychological distress is at a level of danger to self or others, the child's parent and attending oncologist will be immediately consulted to arrange an evaluation at Riley Hospital (Indianapolis site), Children's Mercy Hospital (Kansas City site), Children's Healthcare of Atlanta (Atlanta site), or University of Texas MD Anderson Cancer Center (Houston site) unless the parent indicates a preference for treatment elsewhere. In the event that a parent is judged to be a danger to self or others, the child's primary care oncologist will be consulted to arrange an evaluation, unless the parent indicates a preference for treatment

elsewhere. Again, parents and children will be informed they can stop the session at any time and/or stop their involvement in the study at any time.

## 6.0. MEASURES AND DATA COLLECTION INSTRUMENTS

All measures reflect careful consideration of psychometric properties, sensitivity to change, and response burden. See Appendix 1 for measures and additional psychometrics.

Variable(s)	Measure	# Items	Reliability Evidence	Admin. Schedule	Completed By
Antecedent Factors					
Demographics -parent/child age, parent gender, SES, parent education	Family Information Form	3	N/A	T1	Parent
Prior Distress w/ Hospitalization -parent/child	Prior Illness Experiences Scale (PIES) Abbreviated PTSD checklist (PCL-S)	13 6	.78† .94†	T1 T1, T2, T3	Parent Parent
Disease Characteristics Treatment Characteristics	Diagnosis and Treatment Form Intensity of Treatment Rating Scale Medication Data Form	2 1 7	N/A .95* N/A	T3 T3 T1, T2, T3	Evaluator Oncologist Evaluator
Proximal Mediators					
Child Engagement Parent-Child Interaction	Behavioral Coding Form Behavioral Coding Form	N/A N/A	.85* .85*	Session 3 Session 3	Trained Coder Trained Coder
Distal Mediators					
Family Normalcy Perspective	Family Management Measure (FaMM) Family Life Difficulty Subscale	14	.90†	T1,T2,T3	Parent
Parent Self-Efficacy	Parental Beliefs Scale (PBS)	20	.85†	T1,T2,T3	Parent
Independent Music Play	Parent Report	2	N/A	Sessions 2/3; T2	Parent
Child Outcomes					
Child Emotional Distress	CHQ – Mental Health Subscale	16	.81†	T2, T3	Parent
Child Physical Symptom Distress	Edmonton Symptom Assessment System (ESAS)	3	.69-.80†	T1, T2, T3	Parent
Child Quality of Life	KINDL R	20	.89†	T1, T2, T3	Parent
Parent Outcomes					
Parent Emotional and Traumatic Stress Symptoms	Profile of Mood States-Short Form (POMS) Impact of Events Scale-Revised (IES-R)	37 22	.99** .84-.91†	T1,T2,T3 T1, T2, T3	Parent Parent
Parent Quality of Life	Index of Well-being	9	.93†	T1, T2, T3	Parent
Parent/Child Outcomes					
Family Function	(FACES II)	30	.90†	T1,T2,T3	Parent

†Cronbach's alpha; \*inter-rater reliability; \*\*correlation with POMS

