**Data Collection & Randomization Procedures.** Following consent, the project manager will arrange a time for parents/caregivers to complete baseline (T1) measures during a routine clinic visit, prior to their next scheduled chemotherapy admission. A trained evaluator will administer measures in a quiet/private setting and remain available for questions. The child/parent or caregiver dyad will then be stratified by child age (preschoolers 3-5 years; school-agers 6-8 years) and randomized in blocks of six to the AME or attention control condition by our statistician. After the PI or project manager from the enrolling site receives randomization status from our study statistician, she will inform the parent/child of their randomization status and will then immediately schedule Session 1. Only the

project manager, PI, statistician, and intervener will know the child/parent dyad's randomization status. Evaluators will be blinded.

[figure not shown]
All study condition sessions will be video recorded to facilitate collection of child engagement and parent-child interaction data and monitor treatment fidelity. Sessions 1 and 2 are video recorded to desensitize children/parents to video recording; only Session 3 video data are analyzed for Aim 1. In our previous studies, video recording did not negatively affect participant accrual. An evaluator, blind to randomization status, will administer T2 measures after Session 3. Evaluators will administer T3 measures 30 days (+/- 7 days) post-intervention during a subsequent clinic visit or by telephone. Parent self-reports will be used to monitor use of study condition activities between sessions and between T2 and T3 data collections (Appendix 1).

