## 5.0. RESEARCH DESIGN, METHODS, AND PROCEDURES

**Conceptual Framework.** Our conceptual framework (Figure 1) is based on [name]'s Contextual Support Model of Music Therapy and further informed by Kazak's Pediatric Medical Traumatic Stress Model, which provides a useful heuristic for understanding short and long-term consequences of pediatric cancer treatment for parents and their child. In our conceptual framework, recurring events related to cancer treatment (i.e., hospitalizations, procedures) are viewed as potentially traumatic events. Parent appraisal of events as traumatic or not traumatic is influenced by pre-existing factors, which serve as antecedents in our study.

Published research indicates that higher parent and child distress during cancer treatment and survivorship is related to: 1) demographics (younger child/parent age, female parent gender, and lower socio-economic status/education), 2) higher parent/child distress with prior hospitalizations, and greater traumatic stress symptoms, and 3) disease and treatment characteristics (diagnosis, relapsed disease, greater treatment intensity).

Figure 1: Conceptual Framework

The AME directly targets the proximal mediators of child engagement and parent-child interaction, as well as distal mediators of perceived family normalcy, parent confidence (self-efficacy) about their ability to support their child during treatment, and independent music play between therapist-led sessions.

[figure not shown]
Our study examines proximal and distal mediators of the AME on outcomes for young children (emotional distress, physical symptom distress (exploratory), quality of life), parents (emotional distress, traumatic distress, quality of life), and family function. In addition, we examine moderators of the AME intervention on outcomes (child/parent distress with prior hospitalizations; child age). This study will allow us to determine *how* and *for whom* the intervention works, informing a subsequent trial to examine cumulative impact/efficacy of AME across repeated cancer treatment admissions to manage distress and prevent traumatic stress symptoms in survivorship. Findings will also have implications for use of the CSM-MT to guide development of active music interventions to manage treatment distress in other populations.

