**Treatment Fidelity Strategies.** Our team developed and published treatment fidelity strategies consistent with NIH Treatment Fidelity Workgroup recommendations to ensure treatment integrity, minimize experimental drift, and minimize contamination of the control group. Strategies include: 1) standardized intervention and control condition protocols, study manuals, and training; 2) self- and external monitoring of video-recorded intervention/attention control sessions; 3) self- and external monitoring of audio-recorded evaluation sessions; 4) quality assurance checklists to track protocol deviations; 5) intervener field notes to document duration and frequency (dose), and uptake of study conditions; 6) separate intervener/evaluator conference calls; and 7) weekly study administration team meetings to address any concerns.

**Sources of Materials.** All data will be collected solely for the purposes of this study. Parents will complete a set of study measures three times (baseline, post-session 3, and 30-days post-session 3). We estimate it will take the parent 30 – 45 minutes to complete measures.

All measures will be completed using paper/pencil administration. Once parents complete a set of measures our evaluators will directly enter data into RedCap, a HIPAA compliant web-based data

management system. Paper measures will be secured in a locked cabinet, in a locked office dedicated to our study.

Medical information will be obtained from chart reviews, relevant to diagnosis and treatments. These data will be obtained by our evaluators, all of whom are Children's Oncology Group Certified Research Associates.

Field notes on intervention and evaluation sessions will be completed by music therapist and evaluators using a password protected computers that are connected to a secure web-based server. All study related materials and forms are stored on HIPAA compliant encrypted data management server.

All intervention and attention control sessions will be video recorded, and all evaluation sessions audio recorded to facilitate collection of behavioral outcome data and to monitor fidelity.

A listing of specific measures can be found in Section B and in Appendix 1 of this application. Only the PI and the project coordinator will have access to subject identities; all raw data, including digital audio and video data will be stored according to Indiana University IRB requirements.

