**Missing data and multiple comparisons:** We will compare all baseline variables between subjects who drop out of the study and those who do not using two-sample *t* tests, chi-square tests, or their non-parametric equivalents as appropriate. MPLUS software will incorporate participants who drop out before completion by using the MPLUS imputation method to perform a bias adjustment for missing data under maximum likelihood estimation and the assumption that data are missing at random. If we find that missing data are not missing at random, we will use a pattern mixture modeling approach to address; however, based on our prior studies we expect limited attrition (<15%) and little to no missing data on instruments (<1%). As our primary outcomes are child (CHQ) and parent emotional/traumatic (POMS) distress and other outcomes are considered secondary, we do not plan on adjusting *p* value for multiple comparisons for the primary outcomes but will apply the Hochberg step-up procedure for the secondary outcomes.

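### Diagnosis and treatment intensity are classed as antecedents but recorded only at T3, and neither enters the balance check or any planned model

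*Combined protocol and SAP*

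**What the plan says.** Section 5.0 (Conceptual Framework) describes parents' appraisal of events as "influenced by pre-existing factors, which serve as antecedents in our study". Among the factors that published work links to higher distress it lists "disease and treatment characteristics (diagnosis, relapsed disease, greater treatment intensity").

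The table in Section 6.0 groups three forms under disease and treatment characteristics within the antecedent factors: "Diagnosis and Treatment Form Intensity of Treatment Rating Scale Medication Data Form". The first two, of which the second is the "Intensity of Treatment Rating Scale", are scheduled at T3 only, the third at T1, T2 and T3. The persons completing them are, in the same order, "Evaluator Oncologist Evaluator". Every other antecedent measure in the table includes T1.

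On timing, Section 4.0 states: "Evaluators will administer T3 measures 30 days (+/- 7 days) post-intervention during a subsequent clinic visit or by telephone". On source, Section 5.0 (Sources of Materials) states: "Medical information will be obtained from chart reviews, relevant to diagnosis and treatments".

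Section 7.0 checks balance between arms on demographics and the baseline values of the outcomes, and adjusts for demographics found unbalanced. The outcome models control for the T1 value, age group, site and up to six imbalances carried forward from that check. On dropout the plan says: "We will compare all baseline variables between subjects who drop out of the study and those who do not". Disease and treatment characteristics are not named in any of these steps.

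**The concern.** A variable treated as pre-existing should describe the child before randomisation. A rating of treatment intensity made about a month after the intervention may instead describe treatment given since then, and the plan states no reference date. If such a rating were later used as a covariate, it would have been recorded after the Session 3 mediators and the T2 outcomes that it was meant to help explain.

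With no T1 record, a chance imbalance in diagnosis or intensity would not be seen in the balance check, and neither variable is available as a baseline item when dropouts are compared with completers.

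The larger issue is Aim 1, whose main goal is to test mediation. Randomisation balances the arms, so it supports the effect of AME on the mediators and on the outcomes. It does not balance children with high and low engagement, or parents with high and low self-efficacy. Treatment intensity could plausibly influence both a mediator, such as engagement at Session 3, and distress. If so, it confounds the mediator-to-outcome path whether or not the arms are balanced on it, and the plan has no pre-randomisation measure with which to adjust.

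**Working it through.** **1. Label against schedule (Sections 5.0 and 6.0).**

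| Antecedent item | Scheduled | Completed by |
|---|---|---|
| Family Information Form | T1 | Parent |
| Prior Illness Experiences Scale | T1 | Parent |
| Abbreviated PTSD checklist | T1, T2, T3 | Parent |
| Diagnosis and Treatment Form | T3 | Evaluator |
| Intensity of treatment rating | T3 | Oncologist |
| Medication Data Form | T1, T2, T3 | Evaluator |

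Only the two forms at issue lack a T1 entry. The mismatch is in the table itself and needs no calculation.

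**2. Use in the analysis (Section 7.0).** The plan counts up to 15 variables per outcome model: 6 key predictors + T1 value + age group + site (counted as one) + up to 6 imbalances = 6 + 1 + 1 + 1 + 6 = 15. The six places are for imbalances found in the balance check, which does not include disease or treatment characteristics. So diagnosis and intensity have no route into a model.

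**3. How many dyads could lack the forms (Section 3.0).** The plan's own figure reproduces: 156 / (1 − 0.15) = 183.5, rounded up to 184. Expected losses by T3 are 184 − 156 = 28, and 28 / 184 = 15.2%.
- If the forms are completed only for families who reach T3, up to 28 dyads lack them.
- If they are completed for every randomised dyad whatever the family's attendance, the number is near 0.

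The documents do not say which applies, so the range is 0 to 28.

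**4. Possible gain in precision.** The documents do not say how much outcome variance intensity explains. Let R² be the share of residual variance it explains after the covariates already planned (an assumption). For a simple adjusted group difference, the standard error is multiplied by √(1 − R²).

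| Assumed R² | √(1 − R²) | Fall in standard error |
|---|---|---|
| 0.02 | 0.990 | about 1% |
| 0.05 | 0.975 | about 2.5% |
| 0.10 | 0.949 | about 5% |

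This does not carry over to the Aim 1 indirect effects. Those are products of paths tested by percentile bootstrap, and their standard errors do not shrink by this factor unless every path gains equally. For Aim 1 the reason to adjust is confounding, and the documents give no figure from which to size it.

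**The case against.** The strongest reply is that recording date is not reference date. The forms are completed by an evaluator and an oncologist, not by the parent, and diagnosis and treatment information comes from the chart. A family that stops answering questionnaires does not remove the chart. Diagnosis, and relapse status at enrolment, can be abstracted later and still be baseline values. The intensity rating might also be tied to the treatment planned before randomisation. Section 6.0 refers to Appendix 1 for the measures; that appendix is not in the text available here, so a reference period stated there cannot be excluded.

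Other features may limit what is at stake. Eligibility is restricted to moderate or high treatment intensity, chemotherapy follows common cooperative-group guidelines, site is in every model, and medication data are collected at T1. Any imbalance between arms is a chance event. Since no model uses either variable, no planned analysis currently conditions on a post-randomisation rating.

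Much of this stands. A reader might infer that the forms will be missing for all dropouts, or that neither variable can serve as a baseline covariate. The documents support neither inference: the plan is silent on completing the forms after a family leaves, and diagnosis is recoverable. Nor do they show that intensity predicts dropout.

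Two things remain. The reference date for intensity is unstated in the text, and the commitment to pursue non-completers in Section 7.0 covers outcome data only. In addition, chance balance between arms does not answer the mediation argument, because the confounding there is between mediator and outcome within arms.

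**Conclusion.** The concern holds as a low-cost improvement, not as an error that invalidates an analysis. Two variables that the plan itself calls antecedents are scheduled only after the intervention. As scheduled, neither is on hand at T1 for the balance check or the dropout comparison, and neither enters a model. The problem is firmer for treatment intensity, which can change after randomisation, than for diagnosis.

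The number of dyads without the forms is somewhere from 0 to 28 of 184; quoting 28 alone would overstate what is known. The precision gain is about 1% to 5% of the standard error if R² lies between 0.02 and 0.10, for simple adjusted effects. It would be tempting to turn the upper end into a sample-size equivalent (1 / 0.90 = 1.11, or about 11% more dyads), but that rests on one assumed value and does not apply to the indirect effects. The better-founded argument is control of mediator-outcome confounding in Aim 1. It assumes that intensity affects both engagement (or another mediator) and distress, which is plausible but not quantified in the documents.

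**What to change.** 1. In the Section 6.0 table, schedule the Diagnosis and Treatment Form and the intensity rating at T1. Alternatively, keep later completion but state that both describe status at T1. A T3 update may be kept as a separate variable.
2. State that both are completed for every randomised dyad, including those who leave the study.
3. In Section 7.0, pre-specify baseline treatment intensity as a covariate in the Aim 1 and Aim 2 models, whatever the balance between arms.
4. Add diagnosis and relapse to the dropout comparison, and use them as auxiliary variables in the missing-data model.

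The forms and the staff who complete them stay the same, and no family visit is added. Eligibility screening already requires a judgement on treatment intensity, and evaluators already complete the Medication Data Form at T1. The cost is a schedule change, a few sentences in Section 7.0, and one more covariate, which takes the plan's maximum from 15 to 16 variables if intensity enters as a single term.

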## **1.0 BACKGROUND & RATIONALE**

Emotional distress in parents and their young child (ages 3-8) with cancer during acute treatment is a prevalent, persistent problem associated with physical symptom distress and diminished quality of life and family function. In the longer term, this acute emotional distress is related to traumatic stress symptoms after treatment ends. As many as 58% of parents and 40% of childhood cancer survivors later report traumatic stress symptoms in the moderate to severe range. These young children and parents require palliative care interventions to manage acute treatment distress and prevent secondary psychosocial morbidity, yet a recent systematic review revealed a glaring absence of empirically validated interventions for this age group.

Music therapy, one of the most frequently used arts-based therapies, has become standard palliative care in many pediatric and adult hospitals; however, few studies have examined mechanisms by which music therapy works. Music-based play is a pervasive, spontaneous, and normal aspect of family life that structures and supports meaningful interactions, and is a primary way young children cope with traumatic experiences.

Based on [name]'s music therapy theoretical framework, we developed and tested the Active Music Engagement (AME) intervention, establishing it as a feasible/acceptable intervention that reduces emotional distress in young children hospitalized for cancer treatment. The music therapist-led AME uses music-based play and parent education/support (music play resource kit; tip sheets). The AME builds on existing skills, minimizing the burden of learning new skills during a stressful time when learning can be less efficient. As parents witness intervention benefits for their child and learn how to use normalizing play activities to help manage their child's distress, traumatic reactions to and distressing memories of hospitalization may be minimized for both children and parents. The AME is particularly viable because it is easy to implement and teaches parents/children how to therapeutically use a familiar activity to manage distress.

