### **Aim 1: Examine the effects of proximal and distal mediators of the Active Music Engagement (AME) intervention on outcomes for young children with cancer and parents.**

Hypothesis 1.1: Child engagement and parent-child interaction (proximal mediators) will mediate the effect of AME on perceived family normalcy, parent self-efficacy, and independent parent/child use of music play.

Hypothesis 1.2: Perceived family normalcy, parent self-efficacy, and independent parent/child use of music play (distal mediators) will mediate the effect of AME on child outcomes (emotional distress, quality of life), parent outcomes (emotional distress, traumatic distress, quality of life), and family function immediately post-intervention (Time 2) and 30 days post-intervention (Time 3).

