**Study Design.** This is a two-group, randomized, controlled trial. Children and one parent will be stratified and randomized in blocks of six to the AME intervention or attention control condition (see Study Schema). Child/parent dyads will be stratified by child age (preschoolers 3-5 yrs; school-agers 6-8 yrs). Both conditions are standardized and each group will receive three 45-minute sessions over 3 days. We chose a randomized, controlled trial over a single-group trial as a control group is optimal for ruling out confounding variables that may impact the relationships between the intervention, mediators, and outcomes. For example, a single-group trial requires a dose be measured to represent the intervention since the variable being mediated must have some variation. The dose may be impacted by several unknown factors that could make interpretation of results difficult. Our prior studies suggest that 1) a usual care condition would likely have high attrition and negatively affect study accrual, and 2) our audio-storybooks low dose condition was acceptable without behavioral benefits. Thus, we will use audio-storybooks as our attention control condition. The number of sessions and amount of contact time were selected based on average length of stay and findings from our preliminary studies which found immediate and longer-term (30 days post-intervention) benefit.

As in our preliminary studies, baseline data (Time 1) will be intervention intervention collected after consent. Time 2 data are collected post-Session 3. Parents/children are encouraged to use AME and low dose audio-storybooks activities between sessions and at home following discharge and self-reported frequency and duration of activities will be collected during sessions 2 and 3, and at T3 (30 days post-intervention). Data collection timelines are based on positive findings from our preliminary studies and inform our primary aims which examine mediation. Findings will inform a subsequent trial to examine long term benefits. See Study Schema for assessment timelines.

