## 7.0. STATISTICAL CONSIDERATIONS

As part of Preliminary Study 3, we have already created and successfully implemented a secure web-based system to capture the study data using the REDCap database management system, as well as a telephone log system and participant calendar that will enable the research coordinators to track and schedule participants' visits. We will review and process data using already-programmed multiple verification and edit-checking programs. We will also conduct rudimentary analyses to ensure that the data have been properly collected and to identify any outliers or errors.

Preliminary analyses: Prior to hypothesis testing, we will calculate coefficient alpha as a measure of internal consistency reliability on all multiple-item scales. Construct validity will be assessed by calculating Pearson or Spearman correlations between scales to determine if correlations are in the expected direction. We will assess multicollinearity between the scales for the mediators by examining the correlations above. If any pairwise correlations are 0.7 or higher we will not include both variables in a given model but fit separate models instead and acknowledge this issue in the interpretation. We will also compare the AME group to the attention control group with respect to demographic and baseline outcome variables using two-sample *t* tests, chi-square tests, or Fisher's

Exact tests as appropriate. We will control for any demographic variables that are not balanced in the models below (all models will adjust for baseline outcome). We will also control for site in all models.

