**Main analyses:** For analyses below we will analyze as randomized and attempt to collect outcome data on non-completers, following the intent-to-treat principle. For Aims 1 and 2, each outcome will be modeled separately. Also we will model T2 separately from T3. Thus, there will be a total of 12 models in Aim 1 (6 outcomes x two time points). In Aim 2, two outcomes will be examined and 3 potential moderators at two time points for a total of 12 (2 outcomes x 3 moderators x 2 time points) models. For Aim 1, our primary goal is to test mediation effects. Mediation effects will be estimated in an ANCOVA setting, fitting the appropriate mediation models using MPlus and then testing indirect effects using the percentile bootstrap approach to estimate the indirect effect. The multiple mediation model with three-path mediation effects specifies that the intervention will act through the proximal and distal mediator on the outcome and also have a direct effect on the outcome. Each outcome model will have 6 key predictors (intervention, two proximal mediators, 3 distal mediators), and control for T1, age (3-5 years vs. 6-8 years), site, and any imbalanced baseline covariates found above (allowing for up to 6 imbalances). Thus we will have up to 15 variables in any model. For Aim 2, we will test moderation effects by including the appropriate interaction terms of the potential moderator (dichotomized at the median) with the intervention indicator (AME vs. attention control) in our models. For all models in Aims 1 and 2, we will assess goodness-of-fit (GOF) using standard GOF measures (comparative fit index, root mean square error of approximation, and root mean square residual). For Aim 3, an exploratory aim, we will use ANCOVA to compare changes in child symptom distress at T2 and T3 between intervention and control groups. In light of positive findings, we next will explore models as in Aims 1 and 2 to assess for potential mediation and moderation effects for this outcome.

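### Independent music play is the only distal mediator without a baseline measure, which leaves its path to outcome open to confounding by home music habit

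*Combined protocol and SAP*

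**What the plan says.** Hypothesis 1.2 names three distal mediators: "Perceived family normalcy, parent self-efficacy, and independent parent/child use of music play (distal mediators) will mediate the effect of AME" on the child, parent and family outcomes.

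The measures table in Section 6.0 gives the family normalcy and parental beliefs scales at T1, T2 and T3. Independent music play, a two-item parent report, is scheduled at "Sessions 2/3; T2". The Study Design paragraph of Section 5.0 has a different last time point: "self-reported frequency and duration of activities will be collected during sessions 2 and 3, and at T3 (30 days post-intervention". Neither includes T1.

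Section 1.0 describes the behaviour as common before any intervention: "Music-based play is a pervasive, spontaneous, and normal aspect of family life".

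Section 7.0 says that "all models will adjust for baseline outcome". It lists the other adjustments as "control for T1, age (3-5 years vs. 6-8 years), site, and any imbalanced baseline covariates found above (allowing for up to 6 imbalances"), and the imbalance screen covers demographic and baseline outcome variables. No term represents prior music play. No sensitivity analysis for mediator-outcome confounding is described.

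**The concern.** Families arrive with different musical habits. A family that already plays musically may use the kit more during the stay. It may also differ in distress or family function for reasons unrelated to AME. Within each arm, play and outcome would then be associated even if play had no effect.

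An indirect effect is the product of two paths. AME supplies a kit and coaching intended to raise independent play, so the first path should be non-zero almost by design. Whether the product is declared significant then depends mainly on the second path, which is not randomised. Balance between arms does not help there, because the confounding acts within arms.

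Mediation is the primary goal of Aim 1, and play enters all 12 of its models (6 outcomes x 2 time points). The risk is a published mechanism that partly reflects who the families were before enrolment.

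**Working it through.** **The plan's own figures.** Sample size: 156 / (1 - 0.15) = 183.5, rounded up to 184, as stated. Model size: 6 key predictors + T1 + age + site + 6 imbalances = 15, matching "Thus we will have up to 15 variables in any model". The sum works only if T1 is one variable (the baseline outcome) and site is one term, so it has no slot for the baseline of any mediator.

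**Assumed inputs.** The documents give no effect size for play, no habit correlations and no alpha. I take:
- 78 dyads per arm and a two-sided 5% level;
- an AME effect on play of a = 0.8 SD;
- habit correlating r1 with play and r2 with outcome within arm;
- a true effect of play on outcome of zero.

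**AME-to-play path.** SE = 2/√156 = 0.160, so z = 0.8/0.160 = 5.0. This path is almost always significant, and it is unbiased because habit is balanced by randomisation. A T1 habit measure of reliability w multiplies the SE by √(1 - w·r1²). For r1 = 0.3 to 0.5 and w = 0.6 to 1.0, the SE falls by about 3 to 13%, a modest gain.

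**Play-to-outcome path without the T1 outcome.** The spurious slope is r1·r2, with SE about 1/√156 = 0.080, so z = r1·r2·√156. The chance of a false finding is Φ(z - 1.96) + Φ(-z - 1.96).

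**With the T1 outcome in the model.** If habit correlates equally with the T1 and later outcome, and those two correlate ρ, z is multiplied by about √((1 - ρ)/(1 + ρ)): 0.58 for ρ = 0.5 and 0.42 for ρ = 0.7.

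**With a T1 habit item of reliability w and no T1 outcome.** z = r1·r2·(1 - w)·√156 / √((1 - w·r1²)(1 - w·r2²)).

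| r1, r2 | Spurious slope | No T1 outcome | T1 outcome, ρ = 0.5 / 0.7 | T1 habit item, w = 0.8 |
|---|---|---|---|---|
| 0.5, 0.3 | 0.15 | 47% | 19% / 12% | 7% |
| 0.5, 0.2 | 0.10 | 24% | 11% / 8% | 6% |
| 0.3, 0.2 | 0.06 | 12% | 7% / 6% | 5% |
| 0.3, 0.1 | 0.03 | 7% | 6% / 5% | 5% |
| 0.2, 0.1 | 0.02 | 6% | 5% / 5% | 5% |

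**Simulation at the same N**, over the first three rows, gave false mediation in:
- 11 to 45% of trials with neither the T1 outcome nor other mediators in the model;
- 7 to 18% with the T1 outcome;
- 5 to 13% with the T1 outcome and one proximal mediator correlated with habit;
- 4 to 8% with a T1 habit covariate of reliability 0.8.

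The planned percentile bootstrap behaves similarly or is somewhat less conservative. At r1 = r2 = 0.3 it gave 28% without and 13% with the T1 outcome, against 20% and 10% by the formula. With no AME effect on play it gave at most 4.2%.

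**Which outcomes fall where.** All outcomes except the CHQ have a T1 score in the Section 6.0 table. The CHQ mental health subscale, one of the primary outcomes, is listed at T2 and T3 only. As tabulated, it cannot receive the baseline adjustment that Section 7.0 promises for all models.

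**The case against.** The strongest counter-arguments are these.

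- **The planned model already absorbs much of the bias.** It contains the baseline outcome and the other mediators, including parent-child interaction. This stands. Rates near 45% do not apply to outcomes with a T1 score, and co-mediators related to habit lower the rate further.
- **Every driving input is assumed.** This stands. Section 1.0 says music play is common. It does not say that habit predicts kit use during a three-day course, or that musical families are less distressed. If the correlations are small, there is almost nothing to correct.
- **The mediator exists only after randomisation.** It is play on the family's own initiative between therapist sessions, and the report is described thus: "Parent self-reports will be used to monitor use of study condition activities between sessions". This stands against asking the same items at T1, since no kit exists then. A T1 question on usual home music play is a proxy for habit. The description also leaves unclear whether control families' music play is recorded, since their study activity is audio-storybooks.
- **A baseline item is a partial remedy.** True: reliability below 1 leaves residual confounding. At r1 = r2 = 0.5, an AME effect of 0.5 SD and reliability 0.7, without the T1 outcome, 19% remained in simulation.
- **Appendix 1 may hold more.** It is not in the public text. If it contains a T1 music-play item, only the modelling part of this point remains.

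None of this supplies a measured baseline habit or a sensitivity analysis, so the exposure remains at a smaller size for most outcomes.

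**Conclusion.** The gap is real and its consequence conditional. Independent music play has no T1 measure in either schedule, and no named covariate stands in for habit. Under the stated assumptions (habit 0.3 to 0.5 with play and 0.2 to 0.3 with outcome, AME effect 0.8 SD, N = 156), false mediation through play occurs in about 5 to 18% of trials with the T1 outcome in the model, and up to about 45% without it. The second range concerns the CHQ if the table is right. With smaller correlations the rate is near 5%.

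Four stronger readings might be inferred and are not supported:

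- That habit biases the estimated AME effect on play. Randomisation prevents this; only precision is lost.
- That the high rates apply to all 12 Aim 1 models. They require that no baseline outcome be adjusted for. Rates of 78 to 89% arose only with habit correlations of 0.5 on both sides and no T1 outcome; with it they were 38 to 44%.
- That Hypothesis 1.1 is shown to be affected. There play is the dependent variable, and these calculations do not address it.
- That the other two distal mediators are protected by their T1 scores. The 15-variable count appears not to enter those scores.

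The point does not invalidate the trial. It weakens any claim that play is a mechanism, most of all for the CHQ.

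**What to change.** 1. Add two items to the T1 parent set, before randomisation and in both arms: frequency and duration of usual home music play over a fixed recent window. Place them among other home-activity questions. Describe them as a proxy for habit, distinct from the kit-use report.
2. Name this T1 value in the SAP as a covariate in the play equation and in the outcome equations. One summary score takes the stated maximum from 15 to 16.
3. Reconcile Sections 5.0 and 6.0 on whether the last play report is at T2 or T3, and state whether control families' music play is recorded.
4. Reconcile the CHQ schedule in Section 6.0 with the promise in Section 7.0 to adjust every model for the baseline outcome.
5. Because imperfect reliability leaves some bias, add a sensitivity analysis for mediator-outcome confounding of the play path.

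The cost is small. The parent-completed T1 instruments total 3 + 13 + 6 + 14 + 20 + 3 + 20 + 37 + 22 + 9 + 30 = 177 items, so two more make 179. The downside is slight extra burden and a small risk of prompting control families to play music, which the placement in step 1 limits. The items must be asked before randomisation; a later recall of prior habit could be coloured by the assigned condition.
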